5.1 Administration and/or Delivery of Study Intervention

Smoke-free home PSH resident intervention. Study staff will deliver a one hour, one-on-one counseling to PSH residents that includes: (1) a step-by-step guide on how to voluntarily adopt a smoke-free home, (2) information on SHS and thirdhand smoke, alternative combustible tobacco and nicotine product use, cannabis-tobacco co-use, effects of SHS on kids and pets,⁴⁰⁻

⁴³(3) a worksheet on calculating personal costs related to tobacco use, and (4) pledges to designate one's home smoke-free.

Smoke-free home PSH staff intervention. Study staff will conduct a two-hour training for PSH staff on how to provide referrals to smoking cessation programs using materials previously developed from the UCSF's Rxforchange curriculum for service providers.⁷⁹ PSH staff play an integral role in residents' lives by facilitating access to services, whether they be mental health, substance use or healthcare services. In keeping with that model, our training is directed toward empowering PSH staff to provide referrals to local cessation services using the ask, advise, and refer approach,⁸⁰ which has been shown to increase engagement in cessation treatment. The training will address nicotine addiction, tobacco use among PSH residents, pilot data, brief cessation counseling (ask, advise, and refer), and local resources for cessation. Because PSH resident-PSH staff encounters will take place as part of routine care, we will request permission from a random sample of staff and resident dyads (n=40) to record these interactions to assess fidelity.

Usual care. The current standard of care includes no interventions for smoke-free home adoption or referrals to smoking cessation resources.

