 3. A **Certificate of Confidentiality** obtained from NIH to protect the privacy of participants against most legal discovery requests and to address patients' concerns with privacy due to immigration status or legal repercussions.
 4. Offer participants the option of **meeting at their preferred** time to complete follow-up assessments (e.g., after work, after school, on the weekends) and at a location of their preference in their community (e.g., outdoor locations).
 5. Use of **personalized and culturally sensitive mailings** such as birthdays cards and holiday cards to ensure that patients feel like they are part of our study.
 6. **Community Advisory Board** to include mostly persons with lived experiences of housing instability and living in PSH, housing staff, community members, key homelessness and housing policy makers, and local tobacco control experts who will review and advise on all study stages including intervention and assessment materials (meeting 2x/year).
 7. A study design **grounded in the local culture** based on housing input, housing needs, and experience with providing services to low-income residents in PSH.
 8. Conduct **reminders** (calls/text-messages/e-mails) one week and 24 hours before the brief intervention visit and research assessments. This is to remind participants with busy schedules.
 9. Have an **international toll-free number** for participants to contact us and call in for coaching sessions, even if they travel outside the United States.
 10. **Monetary incentives** to complete the baseline (\$20), and follow-up assessments at 3-months (\$15) and 6-months (\$25), and an additional \$5 for placement of the air nicotine monitor.
 11. **Use of existing procedures to locate patients lost-to-follow up**, including working with housing staff to identify participants so that study staff can meet them at the PSH site to conduct or schedule the research assessment or schedule the intervention session; and obtaining the updated contact information for study participants and their designated contact person.
 12. **Locator Guides** with contact information for the participants, emergency contacts, friends and medical providers.
 13. Conduct **Monthly Interim Re-Contact** calls that are incentivized (\$5 visit) for participants at months in between scheduled visits to thank them for participating, remind them of the study incentives, update Locator Guides, and address any questions.

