 14. Supportive telephone tobacco-use/wellness **health coaching** designed partially for participant retention. Follow-up and re-contact efforts for intervention sessions will include weekly written letters or e-mail, followed by telephone calls (three weekly attempts will be made before shifting to monthly contacts).¹³⁰
 15. Study instruments and intervention materials designed to meet the **literacy needs** of persons with low educational attainment.
 16. **Update participant contact information** in Locator Guides at follow-up assessments, coaching sessions, and interim re-contact calls.
 17. Extra effort **tracking participants lost to follow-up** at homes, shelters, outdoors using paid navigators who had lived experiences of housing instability and living in PSH.

18. Provide patients **\$5 for each telephone session**, or yoked re-contact session to defray cost of cell phone minutes.
19. Designated **tracking/scheduling staff**.
20. Use of laminated **appointment study business cards** with study contact information.
21. Collect **agency contact information** from patients where they might receive social services.
22. **Study Website** with educational materials, community resource links, and contact information for study staff.
23. Making **“home visits” in PSH and/or outdoor locations** for difficult-to-find patients.

6 Study Procedures and Assessments

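### The retention plan offers telephone tobacco coaching without naming an arm, which conflicts with the single counseling session and the usual-care control described in Sections 3.1 and 5.1

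*Combined protocol and SAP*

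**What the plan says.** **Intervention.** Section 3.1 and the abstract name two components: individual counseling for residents and referral training for housing staff. Section 5.1 gives the resident part: "Study staff will deliver a one hour, one-on-one counseling to PSH residents that includes" four listed contents. Telephone coaching is not among them.

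**Control.** Section 3.1 puts wait-list residents on usual care until they cross over. Section 5.1 defines that care: "The current standard of care includes no interventions for smoke-free home adoption or referrals to smoking cessation resources".

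**Retention plan (Section 5.6).**
- Item 9 sets up a toll-free number "for participants to contact us and call in for coaching sessions, even if they travel outside the United States".
- Item 14 lists "Supportive telephone tobacco-use/wellness health coaching designed partially for participant retention" and continues: "Follow-up and re-contact efforts for intervention sessions will include weekly written letters or e-mail, followed by telephone calls".
- Item 16 has contact details updated "in Locator Guides at follow-up assessments, coaching sessions, and interim re-contact calls".
- Item 18 pays $5 for a telephone session "or yoked re-contact session to defray cost of cell phone minutes".
- Item 13 separately describes monthly re-contact calls, also paid at $5, with neutral content: thanks, a reminder of incentives, updated contact details and answers to questions.

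None of these items says which arm it applies to.

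**The concern.** Section 5.6 reads as a list of tasks for study staff, and Section 5.1 reads as the definition of what is being tested. They do not agree on what residents receive before the primary endpoint.

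If coaching goes to everyone, wait-list residents receive tobacco-focused support before their 6-month interview, and the comparator is no longer the usual care that the protocol defines. If it goes to the intervention arm only, the trial tests counseling plus staff training plus coaching, and a difference between arms cannot be attributed to the first two alone. The primary outcome is self-reported and Section 4.7 provides no blinding, so unequal tobacco-focused contact could also affect reporting and retention.

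**Working it through.** The question is mainly one of content, so the relevant sections are set side by side.

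**1. Is coaching just another name for the retention calls?** No. Item 13 already describes those calls and gives them no tobacco content. Item 16 lists coaching sessions and interim re-contact calls as separate kinds of contact. Item 14 says coaching serves retention only in part, which leaves room for another purpose.

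**2. Does coaching appear elsewhere in the protocol?**

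| Place | What it covers | Coaching? |
|---|---|---|
| Abstract; Section 3.1 | Resident counseling, staff training | No |
| Section 5.1 | One hour of counseling; staff training; usual care | No |
| Section 5.2 | Training of study staff for those two components | No |
| Section 5.3 | Adherence to the intervention visit and the staff training | No |
| Sections 6.1 and 6.2 | Schedule and visit lists | No |
| Section 7.1 | Resident measures | No |
| Section 5.6, items 9, 14, 16 | Retention plan | Yes, no arm stated |

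**3. Would exposure be recorded?** Not as written. Section 5.3 tracks attendance at the intervention visit and the staff training. The nearest measures in Section 7.1 are use of cessation aids and referrals offered by housing staff. Neither records coaching from the study team.

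**4. What follows if the list is carried out?**
- Coaching in both arms: wait-list residents are not on the usual care of Section 5.1.
- Coaching in the intervention arm only: Section 5.1 does not describe the intervention delivered.
- Coaching in neither arm: items 9, 14 and 16 describe something that does not happen, and item 18 needs clarifying.

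In every case at least one section has to change.

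**5. Can the consequence be sized?** Section 9.1.1 gives 400 residents, 80% retention, 16 residents per site at 6 months and an intra-site correlation of 0.077.
- Residents per arm at 6 months: 400 × 0.80 / 2 = 160.
- Design effect: 1 + (16 − 1) × 0.077 = 2.155 (stated as 2.16).
- Effective number per arm: 160 / 2.155 = 74.2.
- Detectable intervention rate against 12% at 80% power, two-sided 0.05: 30.3% with unpooled variance, which matches the stated figure, and 30.7% with pooled variance. Pooled power at 30.3% v 12% is 78.5%.

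The plan's own figure therefore reproduces. To go further one would need the effect of coaching in each arm, and the documents give neither.

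**The case against.** **The text may be a leftover.** This is the strongest point on the other side. The plan announces 24 points and lists 23. It offers an international telephone number to residents of supportive housing and at times calls them patients. The table of contents still holds template text. Items 8 and 11 refer to a single intervention visit or session, as Section 5.1 does. On this reading coaching is never delivered. That may be so, and it stands as a real possibility. It does not settle the matter, because the same list is adapted to this trial: it names the housing sites, the air nicotine monitor and the 3- and 6-month incentives. Staff could reasonably follow it.

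**A reader might infer that the control arm is treated.** The documents do not show this. No section says that wait-list residents are coached before 6 months, and the word 'yoked' in item 18 could mean contact-matched calls without coaching in one arm.

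**A reader might infer repeated, paid tobacco coaching.** That joins separate items. Item 14 gives no number of coaching calls, its weekly schedule is for re-contact efforts, and the payment in item 18 is for phone minutes and is not tied to coaching.

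**A reader might infer a loss of power or a bias toward no effect.** This depends wholly on assumption. Suppose coaching raised wait-list adoption from 12% to 16% or 20%. With 74.2 effective residents per arm and the pooled formula:

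| Assumed effect in the intervention arm | Power, control 16% | Power, control 20% |
|---|---|---|
| None (stays at 30.3%) | 54% | 30% |
| Same percentage points (34.3%; 38.3%) | about 73% | about 69% |
| Same odds ratio | about 86% | about 90% |

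The baseline is about 79%, so power falls in the first two rows and rises in the third. The large losses require coaching to help controls only, which nothing in the documents supports.

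**A reader might infer that Aim 2 omits the cost of coaching.** The protocol gives no list of cost items for Aim 2, so nothing shows it excluded.

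**Conclusion.** The contradiction holds. Items 9, 14 and 16 provide for telephone tobacco coaching to participants with no arm stated, and the sections that define the intervention, the control, adherence and the schedule contain none. As written, the documents do not settle what each arm receives before the primary endpoint, and they provide no record from which it could be established afterward.

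The conclusion goes no further than that. Whether coaching is intended, who would receive it and how often are all unknown. The size and direction of any effect on bias or power cannot be computed from the documents, so no power figure should be attached to this point. The finding rests only on the wording of Section 5.6 compared with Sections 3.1, 5.1, 5.3 and 6.1.

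**What to change.** Reconcile items 9, 14, 16 and 18 of the retention plan with Sections 3.1, 5.1, 5.3 and 6.1. It is for the sponsor to say which account is correct.

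- If coaching is not intended, delete it from items 9, 14 and 16, and reword item 18 so that it refers only to retention contacts.
- If coaching is intended, describe it in Section 5.1 by arm, show it in Section 6.1, and log sessions by arm under Section 5.3.
- In either case, keep retention contacts up to the 6-month interview to the neutral content already set out in item 13, the same in both arms.

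The cost is protocol wording and, if coaching is kept, a simple contact log. It should be done before follow-up begins, because exposure that was never recorded cannot be reliably recovered later.

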6.1 Schedule of Activities

Assessments/Procedures	Screening	Study Intervention Period				End of Study Intervention	Follow-up
		Visit 1 /Months 3-12	Visit 2 / Months 6-15	Visit 3 / Months 9-15	Visit 4 / Months 12-20		
Study Visit / Day (Window, # Days)	Visit -1 (Months 1 to 6)					Visit 5 /	Every 3 months
Informed Consent ¹	X						
Inclusion/Exclusion Criteria	X						
Adverse Events	X	X	X	X	X	X	X
Randomization/Assignment to Intervention	X						
Administration of Study Intervention to intervention group	X						
Protocol-Specific Assessments/Procedures	X	X	X	X	X	X	X
Administration of study intervention to wait-list control group			X	X			

¹ Informed consent must be obtained prior to any study-specific procedures and may be obtained prior to the screening window.

6.2 Study Procedures and Assessments

6.2.1 Screening Period / Visit -1 (Months 1 to 6)

After an individual provides informed consent, the following activities will be performed during the Screening Period:

- Inclusion/exclusion criteria review
- Adverse Events assessment
- Protocol-specific assessments/procedures
- Randomization/Assignment to Intervention
- Administration of study intervention

6.2.2 Study Intervention Period

6.2.2.1 Visit 1 (Months 3 to 12)

- Adverse Events assessment
- Protocol-specific assessments/procedures

6.2.2.2 Visit 2 (Months 6 to 15)

- Adverse Events assessment
- Protocol-specific assessments/procedures
- Administration of study intervention to wait-list control groups

6.2.2.3 Visit 3 (Months 9 to 15)

- Adverse Events assessment
- Protocol-specific assessments/procedures for waitlist control group (3-month follow-up)

6.2.2.4 Visit 4 (Months 12 to 20)

- Adverse Events assessment
- Protocol-specific assessments/procedures for waitlist control group (6-month follow-up)

6.2.3 End of Study Intervention / Visit 5

- Placement of the air nicotine monitor (6 month follow-up)
- **Air nicotine assessment procedures.** At 6 months follow-up, we will chose a random sample of participants in the intervention and waitlist control groups, approximately 50% of the sample (N=200), stratified by those reporting a smoke-free home for ≥ 90 days, < 90 days, and not at all to validate self-reports of adoption using passive air nicotine monitoring. These monitors which include a plastic container that contain a sodium bisulfate-coated filter will be purchased from and analyzed via gas chromatography by

the UCSF Helen Diller Family Comprehensive Cancer Center Tobacco Biomarkers Core.¹⁰¹ Staff will obtain permission at the time of informed consent to place monitors in residents' rooms for 7 days,³² within one week of completion of the 6-month interview. Monitors will be placed at least 1 foot away from windows, corners of the room, and exits.³² We will use a threshold of $\leq 0.9743 \mu\text{g}/\text{m}^3$ (sensitivity=69.5% and specificity=81.2%) for a home to be smoke-free.³²

6.2.4 Follow-up

Participants will be followed every 3 months for up to 6 months after discontinuing the study intervention. The following procedures will be performed at each follow-up time point:

- Adverse Events assessment

7 Reporting and Documentation of Results

7.1 Measures and Instruments

Data collection. Questionnaires designed in REDCap will be administered by study staff using an iPad. Intervention and wait-list control participants will complete questionnaires at baseline, 3-, and 6 months follow-up. Wait-list control group participants who cross over to the intervention arm will also complete questionnaires at 9- and 12-months follow-up (3- and 6-months following the intervention).

PSH resident measures. Demographics. We will obtain information on age, sex (sex assigned at birth, current gender), race/ethnicity, education, income from all sources, marital status, and number of smokers in the household. Social determinants of health. We will obtain information on unmet subsistence needs (insufficient access to food, clothing, utilities),⁸¹ social and instrumental support,^{82,83} lifetime history of homelessness, length of stay in current residence, other housing circumstances (e.g., loss of housing), and exposure to urban life stressors.⁸⁴ Alternative tobacco, nicotine product and cannabis use. We will assess ever and past 30-days use and indoor use of e-cigarettes, cigars/little cigars, smokeless tobacco, pipe tobacco, hookah, blunts, and cannabis. Nicotine dependence and smoking cessation. We will assess Fagerstrom's test for nicotine dependence⁸⁵ craving⁸⁶, impulsivity⁸⁷, cigarette smoking behaviors, cigarette quit attempts (ever, in the past year, and since the last visit), length of the last quit attempt, longest time abstinent, and use of cessation aids.⁸⁸ Smoke-free policy measures.⁹ We will assess knowledge of current no-smoking policies, frequency of past-month exposure to SHS, attitudes toward smoke-free policies and indoor cannabis use, knowledge and skills related to smoke-free home adoption, and barriers to smoke-free home adoption.⁹ Measures related to voluntary smoke-free home adoption.^{9,14} We will ask whether participants adopted a smoke-free home voluntarily in the past 90 days and the length of the last adoption, which will be used to define our primary outcome. We will ask those who reported a smoke-free home when they last smoked in their home. We will ask participants to report when they adopted a smoke-free home and when they quit smoking in the past 90 days. We will assess whether they attempted to quit at the same time as they adopted a smoke-free home, adopted a smoke-free home and quit later, or adopted a smoke-free home but did not quit. Expenditures for tobacco use. We will obtain information on the amount of money spent on tobacco in the past week, which we will use to estimate tobacco-related expenditures. Chronic diseases. We

will ask about diagnoses of liver disease, renal disease, cardiovascular disease, hypertension, diabetes, cancer, pulmonary disease, and HIV.⁸⁹ Mental health. We will conduct the Mini International Neuropsychiatric Interview v.6.0 (MINI 6.0)⁹⁰⁻⁹³ to assess DSM-IV and ICD-10 psychiatric diagnoses (lifetime and current diagnosis for depression, bipolar I and II, posttraumatic stress disorder, psychotic disorders, and generalized anxiety disorder). Alcohol and substance use disorders. We will administer the Alcohol, Smoking and Substance Involvement Screening Test version 3.0 (WHO-ASSIST) to assess alcohol and substance use.⁹⁴⁻⁹⁷ To assess alcohol volume consumed, we will administer the Alcohol Use Disorders Identification Test (AUDIT-C).^{98,99} Satisfaction and usefulness of the intervention. At 3- and 6-months follow-up, we will evaluate satisfaction using a Likert scale and usefulness using a previously validated item by asking, 'In the past three months, what role did the intervention play in helping you adopt a smoke-free home or quit smoking?' Evaluating exposure to and use of cessation referrals by PSH staff. At 3- and 6-months follow-up, we will ask residents whether they had encounters with PSH staff where they were offered cessation referrals, the number of such encounters in the past 3 months, satisfaction and usefulness of these interactions, and use of these referrals to cessation services since the last visit. COVID-19 response. **Given that tobacco smoking increases risk of developing COVID-19 and worsens prognosis from COVID-19 if infected**, we will ask participants to describe: (1) ways in which COVID-19 has impacted their tobacco use and cessation behaviors, (2) their awareness of COVID-19, (3) whether they were diagnosed and/or exposed to someone with COVID-19 since the onset of the pandemic, (4) whether they are able to socially distance, (5) their tobacco use and COVID-19 harm perceptions (e.g., perceived risk of COVID-19 to people who are smoking or exposed to SHS), (6) how COVID-19 has impacted rules around smoking in their home, and (7) how COVID-19 has influenced their engagement in the smoke-free home intervention. **We included these questions to explore whether the COVID-19 pandemic has motivated a change in smoking behavior, and whether shelter in place restrictions has impacted participants' ability to smoke outdoors.**

PSH staff measures: Staff will be asked to complete the Smoking Knowledge Attitudes Practices (SKAP) survey at baseline, 3- and 6-months follow-up.^{14,44,69} Staff will report on demographics, role in the facility, smoking history, policies around smoking (e.g., policies restricting e-cigarette and/or cannabis use indoors, provision of on-site cessation services), enforcement of any current smoke-free policies (complaints about the policy, issuance of warnings, or evictions), and barriers to enforcement of current policies. At 3- and 6-months, staff will answer questions on usefulness and satisfaction with the intervention, and whether they referred residents to smoking cessation programs.

8 Adverse Events and Serious Adverse Events

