4.7 Blinding

Not applicable

5 Study Intervention

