9.1.2 Randomization and Blinding

See Section 3.1

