9.3.2 Primary Analysis (or Analysis of Primary Endpoints)

The primary outcome is self-reported voluntary adoption of smoke-free homes for ≥ 90 days at 6 months follow-up. Primary analyses include intention-to-treat comparisons. The 3-level data structure—including PSH housing site, residents, and repeated assessments—will be accommodated by mixed logistic models with random intercepts for sites and residents. The primary outcome will be a binary indicator of adopting a smoke-free home which, in an intention-to-treat analysis, will be regressed onto indicators of experimental groups, categorical time (baseline, 3 months, 6 months), and the group-by-time interaction. Any significant intervention group main effect at follow-up and group-by-time interaction effect will be interpreted and described. If any key demographic or risk factors are imbalanced at baseline, we will include a propensity score-based adjustment.¹⁰⁶⁻¹⁰⁸

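### Outcome interviews are not separated from counselling: staff who take a resident's smoke-free pledge may also record the self-reported primary outcome, a route to differential over-reporting

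*Combined protocol and SAP*

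**What the plan says.** - **Blinding.** Section 4.7 reads, in full, "Not applicable". Section 9.1.2, whose title includes blinding, says only "See Section 3.1". Section 3.1 covers randomisation and is silent on masking.
- **Who counsels.** Section 5.1: "Study staff will deliver a one hour, one-on-one counseling to PSH residents". The session includes "pledges to designate one's home smoke-free".
- **Who collects the outcome.** Section 7.1: "Questionnaires designed in REDCap will be administered by study staff using an iPad". Section 1.4 (COVID-19 protections) allows follow-up visits by Zoom or telephone.
- **The outcome.** Section 9.3.2: "The primary outcome is self-reported voluntary adoption of smoke-free homes", for at least 90 days at 6 months. Section 7.1 derives it from the resident's answers on adoption and its length.
- **Other items at 3 and 6 months.** Section 7.1 also has residents asked "what role did the intervention play in helping you adopt a smoke-free home or quit smoking". No item order is set.
- **Controls.** Under section 4.2, wait-list residents are offered the intervention only after the intervention sites in their block finish 6-month follow-up.
- **Objective check.** Section 6.2.3 places passive air-nicotine monitors with about 200 residents from both arms, stratified by self-reported status, to validate self-report. The stated sensitivity is 69.5% and specificity 81.2%. Section 2.3 lists this as exploratory, and the model in 9.3.2 does not use it. The secondary outcome, by contrast, is verified by expired CO (section 2.2).

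**The concern.** Blinding residents and counsellors to a counselling intervention is not possible, and the plan is not at fault for that. What can be controlled is who asks the outcome question. As written, one undifferentiated group counsels, takes the pledge and later asks whether the home has been smoke-free. A resident may find it harder to admit to smoking indoors to the person who took the pledge. At the primary time point no wait-list resident is in that position, so the pressure is unequal between arms.

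The primary outcome is a self-reported yes/no behaviour. Differential over-reporting therefore adds directly to the intervention-arm rate and, in the primary analysis as specified, looks the same as a treatment effect. A question crediting the intervention with helping the resident, if it came before the outcome items, could add to the pressure.

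**Working it through.** **1. Reproduce the plan's figure.** Inputs from section 9.1.1: 400 residents, 80% retained, 20 sites, 16 per site at 6 months, intra-site correlation 0.077, control rate 12%, two-sided alpha 0.05, 80% power.

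- Followed per arm: 200 × 0.80 = 160.
- Design effect: 1 + 15 × 0.077 = 2.155 (stated as 2.16).
- Effective n per arm: 160 / 2.155 = 74.2.
- For 30.3% v 12%, unpooled: SE = √[(0.12 × 0.88 + 0.303 × 0.697) / 74.2] = 0.0653; z = 0.183 / 0.0653 = 2.80; power = Φ(2.80 − 1.96) = 80%.

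The stated 30.3% is reproduced; with pooled variance the power is 78.5%. The sample-size figure is not in question.

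**2. Over-reporting in the intervention arm alone.** Assume true adoption of 12% in both arms, a share f of intervention-arm non-adopters reporting adoption falsely, and no false reports in controls. The documents give no value for f, so a range is shown.

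Observed intervention rate = 0.12 + 0.88f. Chance of a significant result favouring intervention = Φ(difference / SE − 1.96).

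| f | Observed rates | Difference | False benefit, unpooled | Pooled |
|---|---|---|---|---|
| 0 | 12.0% v 12% | 0 | 2.5% | 2.5% |
| 5% | 16.4% v 12% | 4.4 points | 11.7% | 11.6% |
| 10% | 20.8% v 12% | 8.8 points | 30.8% | 30.3% |
| 15% | 25.2% v 12% | 13.2 points | 55.5% | 54.3% |

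Example, f = 10%: SE = √[(0.12 × 0.88 + 0.208 × 0.792) / 74.2] = 0.0603; z = 0.088 / 0.0603 = 1.46; Φ(1.46 − 1.96) = 31%. The baseline is 2.5%, because a two-sided 5% test errs in the favourable direction half the time.

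The 8.8-point gap is about half of the 18.3-point detectable difference (30.3 − 12). Reaching 30.3% with no true effect would need f = 0.183 / 0.88 = 20.8%.

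**3. Let controls over-report too.** If 5% of control non-adopters also report falsely, the control rate becomes 0.12 + 0.88 × 0.05 = 16.4%.

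- f = 10%: 20.8% v 16.4%; SE 0.0638; z = 0.69; false benefit 10%.
- f = 15%: 25.2% v 16.4%; SE 0.0662; z = 1.33; false benefit 26%.

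The result depends on the difference in over-reporting between arms.

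**4. What the monitors can show.** At the design rates, 160 × 0.12 = 19 control and 160 × 0.303 = 48 intervention residents would report adoption. If half are monitored, that is about 10 and 24. Section 6.2.3 does not state the sampling fraction per stratum, so all 68 or so could also fit within the 200.

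**The case against.** **A counselled, pledged resident knows the expected answer whoever asks.** This stands. The figures above cover all over-reporting, while rostering acts only on the part due to facing one's own counsellor. The documents do not size that part.

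**Controls may misreport too.** This stands. All residents hear the study's purpose at consent and answer the same outcome items. A reader might infer that over-reporting would occur in the intervention arm only; the documents support no more than a differential, and step 3 shows how much that matters.

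**The air-nicotine check exists for this purpose.** This stands in part. Permission is sought at consent, before any outcome answer, which may deter false claims, and the sample covers both arms. A reader might infer that the check is useless; imperfect accuracy weakens a by-arm comparison without emptying it. It remains exploratory, covers about half the residents and does not enter the primary analysis.

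**The overlap and the question order are hypothetical.** A reader might infer that counsellors will interview their own residents face to face, with the usefulness item asked first. The documents do not say so. They permit the overlap without prescribing it, allow remote visits, and describe the adoption items before the usefulness item without fixing an order. Permission alone is enough to justify a safeguard.

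**The entry in 4.7 is a template line.** Perhaps, but no other section supplies the missing separation.

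**Conclusion.** The point holds as a gap in safeguards at outcome assessment. The plan allows the staff who counsel and take the pledge to record the self-reported primary outcome, and only the intervention arm has had counselling and a pledge by then.

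Under no true effect, over-reporting by 5% to 15% of intervention-arm non-adopters alone would raise the chance of a false significant benefit from 2.5% to between about 12% and 55%. With 5% over-reporting in controls, the 10% and 15% cases give about 10% and 26%.

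These figures rest on assumed shares and on a two-proportion z test standing in for the planned mixed logistic model. They show how sensitive the primary outcome is to differential misreporting. They do not measure what role separation would save, and it would be wrong to infer that the fix removes the whole bias. It is a worthwhile improvement because it costs little and acts before the data are collected.

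**What to change.** 1. In 4.7, replace the current entry with a statement that residents and counsellors are unblinded, and describe how outcome collection is protected.
2. In 4.7 and 7.1, roster existing staff so that nobody conducts the 3- or 6-month interview of a resident they counselled. Have the same interviewers cover intervention and wait-list sites within each four-site block.
3. In REDCap, place the primary-outcome items before the satisfaction and usefulness items, and lock that order.
4. Offer self-completion of the outcome items on the iPad already in use. Where literacy or a remote visit requires it, a non-counsellor reads them aloud. This should be an option rather than a rule, since the retention plan in 5.6 itself provides for low-literacy materials.

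Hiding the arm on the form is not worth adding, because whole sites are randomised and the site can reveal the arm.

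The cost is protocol wording, form order and scheduling constraints. The documents give no staff numbers, so the roster's feasibility needs checking. Sample size, visits and intervention are unchanged. Interviewers may still infer the arm from the site, so the bias is reduced and not eliminated.
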